periods: 0–2, 2–6, 6–12 and 12–24 h to evaluate pharmacokinetics. 12–24 h urine samples will be analyzed only at non-zero concentration of PBTZ169 in 6–12 h sample.

During the whole period of blood sampling for pharmacokinetics after the drug administration, the volunteers will be at hospital and will be discharged after all procedures planned in the protocol have been finished, afterwards the monitoring will be continued under out-patient conditions.

Thus, total in-patient period for every cohort will be as follows:

- C1 and C2 - 3 days (including the admission day, day of the test drug administration and 24 h after the drug administration)
- C3 and C4 - 4 days (including the admission day, day of the test drug administration and 48 h after the drug administration)
- C5 - 5 days (including the admission day, day of the test drug administration and 72 h after the test drug administration).

After the discharge from hospital, volunteers from C1–C5 should visit the study center in 5±1 days after the drug administration for follow-up procedures (safety evaluation).

14±1 days after the drug administration, the last visit (Visit 3) will take place in the form of phone contact after which the volunteers will finish the study participation. Thus, total follow-up period will be 14 days after the drug administration for each volunteer.

After the last volunteer from those enrolled in the cohorts of Stage 1 completes the study, safety and pharmacokinetics will be analyzed using the data of all cohorts of a single dose study. Upon the termination of an analysis of the data obtained during the Stage I, an independent Committee for data evaluation and study subjects' safety will be called. The results of the session of the Committee dedicated to the discussion of the data obtained in the first 5 cohorts (the results of the statistical analysis) will serve for preparing a resolution about the safety, tolerance and pharmacokinetics of the drug taken once in the first 5 cohorts. Takin into account the resolution of the independent Committee about the data evaluation and the safety of study subjects, the Sponsor will:

- *Determine the doses of PBTZ-169 for multiple administration during the Stage 2 of the study;*
- *Take the decision on the necessity to adjust blood and urine sampling timepoints ;*
- *Take the decision about the necessity of a study procedure correction.*

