According to the results of the analysis of all the data obtained after the completion of the study by all volunteers from cohorts 1 to 5, a clinical study report will be prepared.

Stage 2 (multiple dosing with dose escalation)

Up to 3 cohorts are planned to be enrolled during the second stage of the study with 6 subjects in each to investigate the drug after multiple administration.

Volunteers complying with the study inclusion criteria will be included successively into the following cohorts for multiple drug administration:

- Cohort 6 (C6) includes 6 healthy volunteers each of whom will receive X* mg of PBTZ169 daily under fasting conditions once a day in the morning at the same time ±15 min for 14 days.
- Cohort 7 (C7) includes 6 healthy volunteers each of whom will receive Y* mg of PBTZ169 daily under fasting conditions once a day in the morning at the same time ±15 min for 14 days.

*The dose of PBTZ-169 will be defined taking into account the results of the data analysis and the conclusions of the independent Committee for data evaluation and study subjects' safety.

The same inclusion criteria will be used to select volunteers into cohorts C6-C7 as those used to select volunteers into Cohorts 1-5.

If two or more volunteers drop out from multiple administration cohorts before the study Day 7 inclusive due to different reasons, except for AE/SAE, according to Sponsor's decision, volunteers can be additionally enrolled by the number of drop outs for whom an additional screening will be performed. Up to 4 back up volunteers are supposed to be additionally required for each of multiple dosing cohorts. If back-up is necessary in multiple dosing cohort, the period of hospitalization and all the study procedures for a back up will be equivalent to those for substituted volunteer.

Screening procedures to include volunteers into each cohort will be performed within 10 days before the drug prescription.

Screening of volunteers into Cohort 7 can be started not earlier than 24 h after all the volunteers from the previous cohort have received the last dose of the drug.

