The drug administration in Cohort 7 can be started not earlier than 7 days after all the volunteers from the previous cohort administer the last drug dose if DLT is reported in less than 50% volunteers from the previous cohort before the latest volunteer is discharged from the hospital. DLT will include any class 3 and more toxicity according to Toxicity Grading Scale for Healthy Adult and Adolescent Volunteers Enrolled in Preventive Vaccine Clinical Trials which is "possibly", "probably" and "definitely" related with the

administration of PBTZ169.

Volunteers included in cohorts C6-C7 are hospitalized in the evening on Day 0 before the first drug dose administration. In the evening of Day 1, every healthy volunteer will take the first dose of the test drug under fasting condition (10 h of night fasting) with 300 mL of bottled water. Afterwards the volunteers will continue daily administration of the test drug at constant dose (depending on the cohort) under in-patient conditions. The drug will be administered daily under fasting condition (10 h of night fasting) o.d. in the morning at the same time \pm 15 and always with 300 mL of bottled water. Food intake is prohibited for the volunteers during 4 hours after the first, 7th and last (14th) dose of the test drug; water intake will be also regulated during this time: not more than 100 mL of bottled water per hour. On the days of the rest drug administrations, the volunteers are prohibited to take food for 2 h after the drug administration; water intake will be also regulated during this time: not more than 100 mL of bottled water per hour. The drug administration period will be 14 days.

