	
concentration determination, additional venous blood will be also sampled for further storage of samples for possible determination of additional parameters.
 
Urine will be sampled from every volunteer in each of cohorts during the first 24 hours after the first and last dosing within the the following time periods: 0–2, 2–6, 6–12 and 12–24 h to evaluate pharmacokinetics. 12-24 h urine samples will be analyzed only at non-zero concentration of PBTZ169 in 6-12 h sample.
 
During the whole period of PBTZ169 administration, the volunteers will be monitored in the hospital; afterwards the monitoring will be continued under outpatient conditions. Total follow-up period will be 14 days after the last drug dose administration for each volunteer.
 
After the discharge from the hospital, volunteers from cohorts C6-C7 should visit the study center in 1 and 2 days for blood sampling at 48 h and 72 h time points and in 7 ± 1 days and 14 ± 1 days for the last drug dosing (the study Day 19 ± 1 and Day 28 ± 1) for follow up procedures (safety evaluation).
 
21 ± 1 days after the last drug dosing (the study Day 35 ± 1) in volunteers from cohorts C6-C7, final visit will be performed in the form of phone contact after which the volunteers will finish the study participation.
 
For patients, who will receive multiple dosing, hospitalization period will be 16 days (including admission day, 14 days of the test drug administration and 24 h of patient monitoring under inpatient conditions after last drug dosing).
 
The results obtained in this study will be used to plan subsequent safety and efficacy clinical studies of PBTZ169.

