	
participate in the study, taking into consideration that PBTZ169 is a novel drug and that the test drug has been manufactured at dose of 40 mg, 40 mg dose will be administered as an initial dose.
 
Maximum dose for this study will be 640 mg as a single dose. Maximum dose can be selected on the basis of lack of negative drug effects when administered at API doses up to 180 mg/kg (HED=30 mg/kg, calculated for a human of 70 kg in body weight - 2100 mg) in rats in subchronic toxicity study, up to 360 mg/kg (HED=60 mg/kg, calculated for a human of 70 kg in body weight - 4200 mg) in rats in acute toxicity study. Thus, selected maximum dose 640 mg is within the range of investigated doses in animals (rats) up to 2100-4200 mg.
 
Dose selection and period of administration for multiple dosing
 
Doses of PBTZ169 for multiple administration will be defined taking into account the results of the data analysis upon study completion by the volunteers from Cohorts 1 to 5, and the conclusions of the independent Committee for data evaluation and study subjects' safety. Two different doses are expected to be chosen for multiple dosing. Good tolerance and safety of the corresponding single dose of the drug will be the defining criteria, including also a determination of a dose-limiting toxicity (DLT) in less than 50% of the volunteers from the respective cohort with single dosing. Presumably, two highest doses among those studied in single administration will be selected, on the condition of a good tolerance of the drug.
 
Multiple administration of PBTZ169 will be performed at hospital under thorough monitoring of volunteers.
 
Taking into consideration that the drug administration period in rabbits and rats was 30 days in the subchronic toxicity study and 180 days in the chronic toxicity study, according to Guidelines for drug evaluation, 2013 (volume I), 14-day period of the test drug administration in this clinical study is justified.

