	
 1. Aggravated allergic history, including presence of at least one episode of drug allergy. 2. Chronic diseases of cardiovascular, bronchopulmonary, neuroendocrine systems, ENT and gastrointestinal, hepatic, renal, blood and cutaneous diseases. 3. Chronic diseases of eyes except for myopia, hypermetropia and mild to moderate astigmatism. 4. Gastrointestinal surgeries (except for appendectomy performed not more than 1 year before screening). 5. Acute infections within less than 4 weeks before screening. 6. Regular drug administration within less than 4 weeks before screening. 7. Regular administration or application (including topical) of hormonal drugs for more than 1 week within less than 45 days before the screening. 8. Administration of drugs exerting evident effects on hemodynamics, hepatic function, etc. (barbiturates, omeprazole, cimetidine, etc.) within less than 45 days before the screening. 9. Positive test for narcotic and psychotropic agents. 10. Donation (450 mL of blood or plasma) within less than 3 months before the screening. 11. Intake of more than 10 U of alcohol per week (1 unit of alcohol is equivalent to 500 mL of beer, 200 mL of vine or 50 mL of strong alcoholic drink) or historical data on alcoholism, narcomania, drug abuse. 12. Mental illnesses. 13. Smoking within half a year before the screening. 14. Previous participation in this clinical study and withdrawal from it due to any reason. 15. Participation in other clinical studies of drugs within less than 6 months before the screening. 16. Planned conception or sperm donation during the study after the test drug administration or during 3 months after the date of the last drug administration.
Withdrawal criteria	
Withdrawal criteria should be considered as follows:
 
 1. Volunteer's refusal to participate in the study at any stage of its performance. 2. Occurrence of adverse event, including serious adverse event: individual intolerance of the test drug, hypersensitivity to the drug ingredients found directly in the drugs administration due to which further participation in the study is not possible. 3. Intolerance of the study procedures by a volunteer. 4. Any event or volunteer's condition which, according to investigator, makes further participation of the volunteer in

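### In the study summary, the Stage 2 DLT criterion decides only whether Cohort 7 starts; no DLT count pauses the remaining daily doses within Cohort 6 or Cohort 7

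*Combined protocol and SAP*

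**What the plan says.** All references are to section 1, Study summary.

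- **Design and methodology, Stage 2.** Cohorts 6 and 7 each have six volunteers dosed once daily for 14 days. After the first dose the text reads: "Afterwards the volunteers will continue daily administration of the test drug at constant dose (depending on the cohort) under in-patient conditions". No DLT condition is attached.
- **Same section, start of Cohort 7.** Dosing may begin at least 7 days after the last Cohort 6 dose, "if DLT is reported in less than 50% volunteers from the previous cohort before the latest volunteer is discharged from the hospital". A DLT is a class 3 or higher toxicity judged at least possibly related to the drug.
- **Same section, number of cohorts.** Up to three Stage 2 cohorts are mentioned, but only Cohorts 6 and 7 are described. On replacements: "Up to 4 back up volunteers are supposed to be additionally required for each of multiple dosing cohorts".
- **Same section, monitoring.** "During the whole period of PBTZ169 administration, the volunteers will be monitored in the hospital". The dose justification adds: "Multiple administration of PBTZ169 will be performed at hospital under thorough monitoring of volunteers".
- **Justification of dose selection.** Stage 2 doses need good tolerance and DLT in under half of the corresponding single-dose cohort. Presumably the "two highest doses among those studied in single administration will be selected, on the condition of a good tolerance of the drug".
- **Withdrawal criteria.** An adverse event leads to withdrawal where it is one "due to which further participation in the study is not possible". The investigator may also withdraw a volunteer for any event or condition, and the sponsor, the investigator or the authorities may terminate the study. No DLT count is named.
- **End of Stage 1.** After the independent Committee's review, one of the sponsor's listed actions is: "Take the decision about the necessity of a study procedure correction".

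**The concern.** The plan treats DLT in half a cohort as reason not to expose new volunteers. The volunteers already in that cohort, who may have many doses left, get no matching protection from the count. For a Cohort 6 that completes as planned, the count closes at discharge, which follows the 14th dose, so it cannot act on Cohort 6's own dosing. In Cohort 7 it has no described use, because no later cohort is described.

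Followed as written, three of six healthy volunteers could have a related grade 3 toxicity, and whether the other three take the next morning's dose would be decided case by case. This is a first-in-human trial, the Stage 2 doses are presumably the two highest studied, and single-dose data cannot show toxicity that builds up over 14 days.

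**Working it through.** **1. Which rules could act on the remaining Stage 2 doses?**

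| Rule in the study summary | What it decides | Is it a DLT count acting during Stage 2 dosing? |
|---|---|---|
| DLT in 2 of the first 3 (Stage 1) | Study termination | No, Cohort 1 only |
| DLT under 50% after single dosing (dose justification) | Choice of Stage 2 doses | No, uses Stage 1 data |
| DLT under 50% in the previous cohort (Stage 2) | Start of Cohort 7 | No, acts after Cohort 6 has finished |
| Independent Committee | Review of Stage 1 data | No, described only after Stage 1 |
| In-patient monitoring | Detection of toxicity | No count |
| Withdrawal and termination | Individual or whole study | Can stop dosing, but at discretion and without a count |

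**2. The threshold as a count.** 2/6 = 33% is below 50%; 3/6 = 50% is not. Three DLTs in six close the gate to Cohort 7.

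**3. Size (illustrative).** The plan has no figure of its own to reproduce.

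Inputs from the documents: 6 volunteers, 14 daily doses, 6 × 14 = 84 planned doses per cohort.

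Assumptions: a 14-day DLT risk q of 10% to 50%; constant daily risk; volunteers act independently; an affected volunteer stops; nobody else is stopped by discretion.

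- Daily risk: p = 1 − (1 − q)^(1/14).
- Risk by day d: F(d) = 1 − (1 − q)^(d/14).
- Third DLT by day d: P(X ≥ 3), X ~ Bin(6, F(d)).
- When the third DLT falls on day d, each unaffected volunteer would on average take a further [1 − (1 − p)^(14 − d)]/p doses, up to their own DLT or day 14. This is summed over the day-by-day chain.

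Worked case, q = 20%:

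- Over 14 days: 1 − (0.8^6 + 6 × 0.2 × 0.8^5 + 15 × 0.04 × 0.8^4) = 1 − (0.2621 + 0.3932 + 0.2458) = 0.0989.
- By day 13, the last day with a dose left to withhold: F = 0.1871, P = 0.0837.
- By day 6: F = 0.0912, P = 0.0123.
- Doses averted: 10.45 per cohort with a third DLT, so 0.0989 × 10.45 = 1.03 averaged over all cohorts.

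| 14-day DLT risk | 10% | 20% | 30% | 40% | 50% |
|---|---|---|---|---|---|
| Third DLT within 14 days | 1.6% | 9.9% | 26% | 46% | 66% |
| Third DLT by day 13 | 1.3% | 8.4% | 22% | 41% | 61% |
| Third DLT by day 6 | 0.2% | 1.2% | 4.1% | 9.5% | 18% |
| Doses averted, per cohort with a third DLT | 9.7 | 10.5 | 11.3 | 12.3 | 13.3 |
| Doses averted, averaged over all cohorts | 0.15 | 1.0 | 2.9 | 5.6 | 8.7 |
| Further DLTs prevented, averaged over all cohorts | 0.001 | 0.016 | 0.07 | 0.20 | 0.42 |

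**4. Sensitivity to timing.** Per cohort with a third DLT, 22 to 25 doses are averted if all the risk falls in days 1 to 7, and 4 to 6 if it falls in days 8 to 14. If the third DLT comes on day 3, the three unaffected volunteers have 3 × 11 = 33 scheduled doses left.

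**The case against.** **Only the summary is available.** A summary need not carry stopping procedures. This stands: a reader might infer that the whole protocol lacks a rule, and the text cannot show that.

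**Judgement already covers the risk.** Volunteers are in hospital throughout dosing, the investigator can withdraw anyone, and the study can be terminated. A reader might infer that volunteers must keep dosing, or are unprotected, after a DLT. The documents do not support that, and in practice clinicians would probably stop after three related grade 3 toxicities. What remains is that none of these powers refers to the count, so nothing requires a pause.

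**The benefit is modest.** This also stands. The averted doses are upper bounds with respect to discretion, since any discretionary stop for the unaffected volunteers reduces them. At risks of 10% to 20% they average one dose per cohort or fewer. Higher risks are not expected, because the doses must first be well tolerated after single dosing.

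**A pause costs pharmacokinetic data.** It does, and this is counted under the fix.

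**A wider rewrite would be disputable.** It is tempting also to recast the Cohort 7 condition as a fixed count, or to require every volunteer with a DLT to stop. The first would tighten a criterion the sponsor has stated whenever replacements are dosed (three DLTs among eight dosed is 37.5%). The second would remove volunteers for toxicity only possibly related, and drop-outs due to adverse events are not replaced. Neither is needed to close the gap.

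**Conclusion.** The point holds for the study summary: the sponsor's own 50% threshold protects volunteers not yet dosed, but no count protects those still being dosed in Cohort 6 or Cohort 7. It is a cheap improvement worth considering and does not show that the trial is unsafe.

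Its value lies in the unexpected case. Under the stated assumptions the pause would be triggered with doses still to withhold in 1.3% of cohorts at a 14-day risk of 10%, 8.4% at 20%, and 22% to 61% at 30% to 50%. These figures rest on assumed risks, constant daily risk and independence between volunteers. The dose figures also assume no discretionary stop and shift with the timing of toxicity. Confidence is medium because later protocol sections may already contain a rule; if so, a cross-reference is enough.

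**What to change.** Add to the Stage 2 text:

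> When a third volunteer in a multiple-dose cohort has a DLT (50% of the planned six), no further dose is given to any volunteer of that cohort until the sponsor and investigator have reviewed the data and recorded a decision to resume or end dosing. Safety follow-up continues.

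Leave the Cohort 7 condition as it is, and leave individual stopping after a DLT to the existing withdrawal criteria. Discretion to stop earlier is unaffected. The sponsor's procedure review between the stages is a natural moment to add it.

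Costs:

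- **Operations.** DLTs must be counted on the same day, before the next morning's dose. Three centres are planned, so the count must be pooled if one cohort is dosed at more than one.
- **No resumption.** The 14th-dose steady-state profile is lost in 1.3/8.4/22/41/61% of cohorts at risks of 10/20/30/40/50%. The planned attempt to sample withdrawn volunteers on the 14th-dose schedule does not replace it. In 0.2/1.2/4.1/9.5/18% (third DLT by day 6) the remaining volunteers also miss the seven doses needed for the multiple-dose pharmacokinetic population. If all the risk falls in days 1 to 7, this last figure is 1.1/7.0/19/36/55%.
- **Resumption.** The gap interrupts the constant daily regimen behind Ctrough and AUCss, so the affected profiles would need to be flagged.

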Each healthy volunteer from the main groups of cohorts C1-C5 will receive only one dose of the test drug in the morning under fasting conditions (10 h of night fasting) with 300 mL of bottled water. On the day of administration, water intake is ad libitum, except for 1 h within the drug administration during which water intake is prohibited and for 4 h after the drug administration (water intake is prohibited during the first hour, water intake will be limited by 100 mL of bottled water ever hour for the successive 3 h). Food intake will be prohibited for 4 h after the drug administration.

Volunteers from cohorts C1 and C2 will have their venous blood samples taken to determine PBTZ169 concentration before the drug administration: -5 min, 0 min, afterwards at the following time points after the drug administration: in 0:10, 0:20, 0:30, 0:45, 1:00, 1:30, 2:00, 2:30, 3:00, 3:30, 4:00, 5:00, 6:00, 8:00, 10:00, 12:00 and 24:00 (h:min).

Volunteers from Cohort 3 will have their venous blood samples taken to determine PBTZ169 concentration before the drug administration: -5 min, 0 min, afterwards at the following time points after the drug administration: in 0:10, 0:20, 0:30, 0:45, 1:00, 1:30, 2:00, 2:30, 3:00, 3:30, 4:00, 5:00, 6:00, 8:00, 10:00, 12:00, 48:00 (h:min).

Volunteers from Cohort 4 will have their venous blood samples taken to determine PBTZ169 concentration before the drug administration: -5 min, 0 min, afterwards at the following time points after the drug administration: in 0:10, 0:20, 0:30, 0:45, 1:00, 1:30, 2:00, 3:00, 4:00, 5:00, 6:00, 8:00, 10:00, 12:00, 24:00 and 48:00 (h:min).

Volunteers from Cohort 5 will have their venous blood samples taken to determine PBTZ169 concentration before the drug administration: -5 min, 0 min, afterwards at the following time points after the drug administration: in 0:10, 0:20, 0:30, 0:45, 1:00, 1:30, 2:00, 3:00, 4:00, 5:00, 6:00, 8:00, 10:00, 12:00, 24:00, 48:00 and 72:00 (h:min).

At every time point of blood sampling for PBTZ169 concentration determination, additional venous blood will be also sampled for further storage of samples for possible determination of additional parameters. Additional blood can be sampled to control the current parameters to assure safety of volunteers.

Urine will be sampled from every volunteer in each of cohorts during the first 24 hours after dosing within the the following time

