Before and after the administration of the first, 7th and last (14th) dose of the test drug, venous blood will be taken from the volunteers to determine PBTZ169 concentration at the following time points: before the first drug dose administration: 0 min (before the drug administration) and for 24 h after the administration of the first, 7th and last (14th) dose of the test drug in: 0:15, 0:30, 0:45, 1:00, 1:30, 2:00, 3:00, 4:00, 6:00, 8:00, 10:00, 12:00, 24:00 (h:min after the drug dosing). 24 h point after the administration of 1 and 7 drug doses should be taken before the successive doses. During drug administration days 3-6 and 9-13, venous blood will be daily taken at 0 min time point (before the drug administration) to determine PBTZ169 concentration. Blood will be sampled at 48 h and 72 h time points after the administration of the last (14) drug dose.

The deviations from the specified time by 10 min to one or another side (\pm 10 min) are acceptable for the following time points: 24 hours for administration of the first, 7th and last (14th) doses of the test drug. For 48 h and 72 h time points after the last (14th) dose administration, deviation from the specified time by 20 min to one or another side (\pm 20 min) is acceptable. For the rest time points, blood sampling after the test drug administration can deviate by not more than 2 min to one or another side (\pm 20 min).

In case of preterm withdrawal from the study, if there is no risk for a volunteers, attempts to sample their blood according to schedule for the last (14) dose will be taken.

At every time point of blood sampling for PBTZ169

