Dose and administration route	
Single oral:
 
 • Cohort 1 — 40 mg • Cohort 2 — 80 mg • Cohort 3 — 160 mg • Cohort 4 — 320 mg • Cohort 5 — 640 mg 
Multiple oral
 
 • Cohort 6 — X* mg/day • Cohort 7 — Y* mg/day 
*The dose of PBTZ-169 will be defined taking into account the results of the data analysis and the conclusions of the independent Committee for data evaluation and study subjects' safety.

Administration period	Single administration in the morning at a fasting state for volunteers from cohorts C1-C5. For volunteers from cohorts C6-C7: daily drug administration o.d. in the morning at a fasting state at the same time±15 min for 14 days.
Reference drug	Not applicable.
Respective therapy	Not applicable.
Primary and secondary variables	
Safety and tolerance variables evaluated
 
 • Adverse events • Changes in vital signs • Results of laboratory analyses (complete blood count, blood biochemistry, urinalysis) • Results of ECG • Results of physical examination 
Pharmacokinetic parameters evaluated (single dosing)
 
 • Maximum concentration (C_{max}) • Time to maximum concentration (T_{max}) • Area under the concentration-time curve from 0 to last blood sampling (t) (AUC_{0-t}) • Area under the concentration-time curve from zero to infinity ($AUC_{0-\infty}$) • Ratio AUC_{0-t} to $AUC_{0-\infty}$ ($AUC_{0-t}/AUC_{0-\infty}$) • Total clearance (Cl) • Renal clearance (Cl_{ren}) • Distribution volume (V_d) • Half-life ($T_{1/2}$) • Mean retention time (MRT) • Absorption rate (C_{max}/AUC_{0-t})

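### Stage 2 wording puts the first dose in the evening of Day 1, against its own morning-dosing and 24 h sampling rules; this is a minor correction, with two smaller slips (sampling window, Day 19 visit) to fix with it

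*Combined protocol and SAP*

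**What the plan says.** All the text is in section 1, Study Summary.

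- **Time of dose 1** (Design and methodology, Stage 2): "In the evening of Day 1, every healthy volunteer will take the first dose of the test drug under fasting condition". The same sentence asks for a 10 h overnight fast.
- **Dosing rule for Cohorts 6 and 7** (same row): "once a day in the morning at the same time ±15 min for 14 days". Two sentences after the evening instruction, daily dosing is again "o.d. in the morning at the same time". The Administration period row repeats it: "daily drug administration o.d. in the morning at a fasting state at the same time±15 min for 14 days".
- **Admission**: "Volunteers included in cohorts C6-C7 are hospitalized in the evening on Day 0 before the first drug dose administration".
- **24 h sample**: "24 h point after the administration of 1 and 7 drug doses should be taken before the successive doses".
- **Daily pre-dose samples**: "During drug administration days 3-6 and 9-13, venous blood will be daily taken at 0 min time point". Days 2 and 8 are not in this list.
- **Parallel Stage 1 wording**: each volunteer "will receive only one dose of the test drug in the morning under fasting conditions (10 h of night fasting) with 300 mL".
- **Sampling window**: for Stage 2 samples other than the 24, 48 and 72 h points, one sentence limits the deviation to 2 min in words and to ±20 min in its bracket.
- **Calendar**: the hospital stay is 16 days. Contacts at 7±1, 14±1 and 21±1 days after the last dose are labelled Day 19±1, Day 28±1 and Day 35±1.

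**The concern.** The time of the first dose is an operative instruction. Taken literally, it conflicts with three statements of morning dosing, with the overnight fast in its own sentence, and with the rule that the 24 h sample comes before dose 2. A site that followed it would give the first two doses of a first-in-human multiple-dose regimen well under 24 h apart, and the end of the first-dose profile would be mixed with dose 2.

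The other two slips are of the same clerical kind. One leaves it unclear which limit defines a sampling deviation. The other gives a study day that does not match the interval beside it.

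**Working it through.** **1. The plan's own calendar.** Dose 1 on Day 1 and 14 daily doses put the last dose on Day 1 + 13 = Day 14.

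- Stay: Day 0 (admission) + Days 1–14 + Day 15 (24 h of monitoring) = 16 days. Agrees.
- 14 days after the last dose: 14 + 14 = Day 28. Agrees.
- 21 days after the last dose: 14 + 21 = Day 35. Agrees.
- 7 days after the last dose: 14 + 7 = Day 21. The plan says Day 19. Does not agree.

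The window of 7±1 days is Days 20–22, and Day 19±1 is Days 18–20. Only Day 20 lies in both.

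**2. Can an evening dose 1 be combined with the other rules?** The documents give no clock times. Assume evening is 18:00–22:00 and morning is 07:00–10:00.

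- *Dose 2 on the morning of Day 2.* The shortest gap is 22:00 to 07:00 = 9 h; the longest is 18:00 to 10:00 = 16 h. The 24 h sample then falls 24 − 16 = 8 h to 24 − 9 = 15 h after dose 2, so it cannot precede it.
- *Dose 2 on the morning of Day 3.* The sample would precede dose 2, but Day 2 has no dose. The last dose moves to Day 3 + 12 = Day 15, the stay to 17 days, and the 14- and 21-day contacts to Days 29 and 36, against the stated 16 days and Days 28 and 35.
- *Evening dosing on every day.* This meets the sampling rule and breaks the morning rule on all 14 days.
- *Fast.* Ten hours before 18:00–22:00 is 08:00–12:00, so the fast would run through the day, not overnight.

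With a morning dose 1, the gap to dose 2 is nominally 24 h and the 24 h sample doubles as the Day 2 pre-dose sample. That explains why Day 2 is missing from the pre-dose list.

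**3. What would be affected if the word were followed.** Samples are scheduled at 0:15, 0:30, 0:45, 1:00, 1:30, 2:00, 3:00, 4:00, 6:00, 8:00, 10:00, 12:00 and 24:00. Urine is collected over 0–2, 2–6, 6–12 and 12–24 h. Assume a blood sample due at the moment of dose 2 is drawn just before it.

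| Gap to dose 2 | First-dose blood containing dose 2 drug | First-dose urine containing dose 2 drug |
|---|---|---|
| 12–16 h | 24 h | 12–24 h |
| 10 to under 12 h | 12 h, 24 h | 6–12 h, 12–24 h |
| 9 h | 10 h, 12 h, 24 h | 6–12 h, 12–24 h |

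The 12–24 h urine is analysed only if the 6–12 h sample is non-zero, so that part is conditional. The dose 14 profile, sampled to 72 h with its own urine collection, is unaffected.

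**4. Sampling window.** The first four post-dose samples are 15 min apart. A ±20 min window is longer than that spacing. For the 0:15 sample it would start at 15 − 20 = −5 min, before the dose. A ±2 min window causes no overlap. Sampling within 2 min meets both figures.

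**The case against.** The best reply is that the document resolves the slip itself. Morning dosing is stated three times for these cohorts, the disputed sentence calls for an overnight fast, admission is the evening before, and the Stage 1 counterpart says morning. A site would have to override all of this to dose in the evening. That stands, and it is why the point is minor. It does not make the sentence correct, and nothing in the available text corrects it. That text is the Study Summary; whether a fuller dosing section reads correctly cannot be judged from it.

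A reader might infer that first-dose exposure, renal clearance and half-life would be badly distorted. The documents do not support a figure: they give no absorption rate, half-life, clock times or formula for renal clearance, and the schedule in question was not intended. The listed parameters are not tied to dose 1, and dose 14 can supply half-life, elimination constant and renal clearance.

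A reader might also infer that the multiple-dose pharmacokinetic population would change. It would not: membership needs at least seven doses and a concentration after the first and seventh, and evening dosing removes neither.

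The window and visit-day slips can be satisfied as written, by sampling within 2 min and visiting on Day 20. That is fair, and neither adds to the severity. The ±20 min may simply repeat the 48 h and 72 h window stated just before it.

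**Conclusion.** The point holds as a minor correction to operative Stage 2 rules that are wrong as written. An evening dose 1 cannot be reconciled with once-daily morning dosing, the sample-before-dose-2 rule and the stated calendar. That conclusion needs no pharmacokinetic assumption. The 9 to 16 h gap rests on assumed clock times, but any ordinary evening-to-morning interval is well under 24 h.

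The intended reading is clear and the practical risk is low. If the word were followed, the loss would be confined to the end of the first-dose blood profile and the later first-dose urine. Day 19 is an arithmetic error for Day 21, and the 2 min versus ±20 min conflict is a wording error.

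The statement that total follow-up lasts 14 days after the last dose, beside a final phone contact at 21±1 days, may mean clinic follow-up before an exit call. It needs clarifying but is not counted as an error here.

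**What to change.** In the Stage 2 text under Design and methodology:

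1. Change the time of dose 1 from the evening to the morning of Day 1.
2. Change the bracketed ±20 min for the remaining sampling points to ±2 min. Leave the separate ±20 min window for the 48 h and 72 h samples as it is.
3. Change Day 19±1 to Day 21±1.
4. As a clarification, say whether the 14-day follow-up means clinic follow-up only or should read 21 days to include the phone contact.

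Make the changes before Cohort 6 is dosed. The sponsor's decision on procedure corrections after Stage 1 is a planned occasion. The cost is a few words, with no added visits, samples or volunteers.
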